## 9.2 Objective 2 Analysis Plan

**Objective 2:** Identify additional predictors of differential treatment response using light phenotype data.

This exploratory analysis will assess whether additional patient reported outcomes captured in clinical settings can improve the prediction of differential treatment response. First, we will assess the functional forms of the predictors through univariate summaries and assess multicollinearity through pairwise Spearman correlation coefficients. Then, we will fit regularized regression models for the primary pain outcome (PROMIS pain interference score) using observations from time points T3 and T4. We will utilize adaptive elastic net (AENET) to induce variable selection while accommodating groups of correlated predictors. Given the exploratory nature of this objective, that

trial patients may have just failed other treatments prior to entering the study, and the need for as much data as possible for the proposed methods, we will treat observations from time points T3 and T4 as independent rather than as repeated measures and adjust for potential effects of stage 1 treatment on observations at T4. We will consider the selection of a treatment interaction into the model as weak evidence for treatment effect modification, and we will conduct hypothesis testing for strong evidence of treatment effect modification. The analysis will be repeated for the secondary pain outcomes (Pain Intensity (PEG) and Patient Global Impression of Change (PGIC)).

Let  $Y_{ti} \in \mathbb{R}$  denote subject  $i$ 's PROMIS pain interference score at time  $t \in \{2, 3, 4\}$ ,  $R_i$  denote response status at T3,  $A_{ti}$  be a vector denoting treatment assignment for  $t \in \{2, 3\}$ , and  $X_{2i}$  denote the vector of baseline variables for subject  $i$  at time point T2 (sex, age, BMI, race, education, and the baseline outcome). Let  $Z_{ti}$  be a vector denoting the additional (clinical/patient reported) predictors and their treatment interactions for subject  $i$  and  $t \in \{2, 3\}$ . We assume

$$E[Y_{ti}] = X_{2i}^T \beta + A_{(t-1)i}^T \phi + I(t = 4) * [R_i A_{2i}^T \varphi_R + (1 - R_i) A_{2i}^T \varphi_{NR}] + Z_{(t-1)i}^T \gamma,$$

and we apply Ridge and adaptive Lasso penalties to the main effects and treatment interactions of the additional predictors. That is, we estimate model parameters by minimizing the sum of squared errors subject to the constraint  $(1 - \alpha) \sum_j \widehat{w}_j \cdot |\gamma(j)| + \alpha \sum_j \gamma(j)^2 \leq t$ , where  $\gamma(j)$  denotes the  $j^{th}$  element of  $\gamma$ . We estimate the tuning parameters  $\alpha$  and  $t$  using 5-fold cross-validation to minimize prediction error and estimate  $\widehat{w}_j = |\widehat{\gamma}_{ENET}(j) + \frac{1}{n}|$ , where  $n$  is the total number of T3 and T4 observations and  $\widehat{\gamma}_{ENET}(j)$  represents the corresponding estimate of  $\gamma(j)$  from a standard elastic net model. Lastly, we obtain AENET parameter estimates using the R package *gcdnet*.

For any treatment-phenotype interactions selected into the fitted model, we will conduct null hypothesis testing. We will use two-sided Wald tests based on standard error estimates from AENET. Using the fitted model, we will also obtain predicted outcomes under each of the four treatment options for all individuals. We will identify the treatment option which maximizes the predicted outcome for each individual and then form up to four subgroups of patients with the same optimal treatment. We will conduct descriptive analyses to compare the characteristics of these subgroups and generate hypotheses for future research based on any baseline patient phenotypes which may be useful for determining optimal initial treatment.

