## 5.4 Inclusion-Exclusion Criteria and General Study Population

### 5.4.1 Participants

Subjects who are ages 25-70 years and who are being seen at Michigan Medicine will be recruited.

Diversity in race and ethnicity is anticipated. All races and ethnicities will be considered for inclusion in the study. Enrollment will be defined as the number of participants consented and randomized into the 4 treatment arms. This study will enroll 408 participants (up to 102 into each intervention) and it is expected that approximately 500 participants may be consented to meet enrollment. Enrollment will be stopped when this enrollment goal is met.

There will be two sets of inclusion and exclusion criteria. The first set is for enrollment into the research project for all participants. The second set represents additional exclusion criteria that are necessary for the safe and valid conduct of the deep phenotyping protocol (subset n=160).

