## Statistical Analysis Plan

phenotype. To address this aim, null hypothesis of regression coefficients will be used. We will use two-sided Wald tests to assess whether the hypothesized differential treatment responses are consistent with the clinical trial data. Let  $\theta$  denote a treatment-phenotype interaction (i.e., one of the elements of  $\psi_2$ ). The Wald test statistic testing  $H_0: \theta = 0$  is given by  $W = \frac{\theta}{SE(\theta)}$ . We will reject the null hypothesis at approximately the 95% level when  $|W| \geq 2$ .

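### Exploratory Objective 2 tests AENET-selected interactions in the data that selected them and grades the result as strong evidence

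*SAP*

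**What the plan says.** SAP 9.2 fits a penalised regression of PROMIS Pain Interference on treatment, baseline covariates and "the additional (clinical/patient reported) predictors and their treatment interactions". The penalties are tuned "using 5-fold cross-validation to minimize prediction error". Then: "For any treatment-phenotype interactions selected into the fitted model, we will conduct null hypothesis testing". The method is "We will use two-sided Wald tests based on standard error estimates from AENET".

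The section sets two grades of evidence. Selection of an interaction is weak evidence. Beyond that, "we will conduct hypothesis testing for strong evidence of treatment effect modification". It describes no held-out patients, no sample split and no correction for selection.

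Other relevant text:
- On the stacked rows, 9.2 says "we will treat observations from time points T3 and T4 as independent rather than as repeated measures". By contrast, 9.1.1 uses robust standard errors for repeated measures.
- 9.2 states no significance level. The only rule is in 9.1.1: "We will reject the null hypothesis at approximately the 95% level when" |W| is at least 2.
- The analysis is repeated for PEG and PGIC.
- 9.2 calls the objective exploratory and says that it will generate hypotheses.
- SAP 7.5 declines formal multiplicity control, prefers confidence intervals and effect sizes to p-values, and promises cross-validation of interactions where appropriate.

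**The concern.** The second grade looks like a further hurdle but is not an independent one. AENET keeps an interaction because its estimate is large in these patients. Testing the kept terms in the same patients asks again a question that selection has already partly answered. Even with no true interaction, the tested terms are the extreme ones, and the usual Wald reference distribution does not apply to them. The cross-validation in 9.2 chooses the penalties and does not check the tests.

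The trial's purpose, in SAP 7.5, is to nominate phenotype-treatment combinations for later study. An interaction marked as strong evidence would go to the front of that list, and later trials could be planned on noise.

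**Working it through.** **The plan's own figure.** The SAP gives no error rate, power or number of tests for Objective 2. Its design figure (6.1) is at least 80% power for a correlation of 0.28 in one arm of 102, two-sided 5%. Fisher's z gives power = Φ(atanh(r)·√(n−3) − 1.96) = Φ(0.2877 × 9.950 − 1.96) = Φ(0.902) = 81.7%, so it reproduces. It concerns a single phenotypic variable and says nothing about tests after selection. The 9.1.1 rule, |W| ≥ 2, is a two-sided level of 4.55%.

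**Inputs from the documents.** "This study will enroll 408 participants (up to 102 into each intervention"), so T3 and T4 give up to 2 × 408 = 816 rows. Other inputs are 5-fold tuning, T3 and T4 treated as independent, and missing data expected not to exceed 15% (SAP 7.4).

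**Assumptions, because the documents are silent.**
- 10 or 25 candidate predictors, giving 40 or 100 interaction columns (75 with 25 predictors and three treatment contrasts).
- Correlation of 0.3 between predictors and 0.5 between a patient's residuals.
- 15% responders at T3.
- Cut-off 1.96.
- Inverse adaptive weights. The printed weight has no inverse exponent, which may be a typesetting loss.
- Three standard error versions, because 9.2 gives no formula: shrunken estimate over asymptotic error, shrunken estimate over sandwich error, and least-squares refit of the selected terms.

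**Check.** For each setting, 200 trials were simulated with every true interaction zero, applying elastic net, adaptive elastic net and Wald tests of the selected interactions in the same data. Monte Carlo standard error is at most √(0.25/200) = 3.5 points. The prognostic settings give five predictors a main effect of 0.1 SD each.

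Percentage of trials with at least one selected interaction passing, primary outcome only:

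| Setting | Asymptotic | Sandwich | Refit | Selected terms passing (sandwich / refit) |
|---|---|---|---|---|
| No effects, 25 predictors | 31.5 | 36.0 | 35.5 | 65 / 59 |
| No effects, 10 predictors | 25.5 | 33.5 | 32.0 | 47 / 42 |
| No effects, 25 predictors, zero within-patient correlation | 23.5 | 24.5 | 24.5 | 54 / 47 |
| Prognostic, 25 predictors | 51.0 | 87.5 | 73.5 | 49 / 37 |
| Prognostic, 25 predictors, 15% missing | 53.5 | 83.5 | 73.5 | 47 / 36 |
| Prognostic, 25 predictors, three contrasts | 50.5 | 84.0 | 73.5 | 48 / 38 |
| Prognostic, 10 predictors | 45.0 | 75.5 | 66.0 | 41 / 34 |

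**Reading the table.** With no effects and 25 predictors, tuning selected at least one interaction in only 37.5% of trials, which caps the trial-level rate. With prognostic main effects it did so in 90.5%, with a mean of 5.1 terms. For the asymptotic version, the share of selected terms passing follows from rounded means: 0.6/3.8 = 16% at the lowest (10 predictors, prognostic) and 0.6/1.6 = 38% at the highest (25 predictors, no effects). All versions are well above 5%.

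**Cross-check.** A separate, simpler simulation used 20 candidates, two prognostic main effects, a plain elastic net and a refit. It gave 34% to 36% of selected terms and 65% to 76% of trials, in line with the prognostic rows.

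**Held-out testing.** Selection in half the patients and testing in the other half at 5% per term (25 predictors) gave at least one false positive in 8.5% of trials with no effects and 25.5% with prognostic effects. Bonferroni over the selected terms reduced these to 0.5% and 5.0%. The remainder before correction is ordinary multiplicity: the median number selected in the prognostic split was 5, and 1 − 0.95⁵ = 22.6%.

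**The case against.** The strongest defence is that 9.2 presents the work as exploratory and SAP 7.5 is candid about multiplicity, intervals and cross-validation. That stands as a defence of exploring many interactions without familywise control. It does not cover this test, because each single test is off its level after selection, before multiplicity is counted. Intervals built from the same post-selection estimates and standard errors share the fault. Section 9.2 does not apply the promised cross-validation to the tests, and an exploratory label sits badly with a pre-specified grade of strong evidence.

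A second objection concerns size, and much of it stands. The candidate count, the standard error formula and the strength of prognostic effects are all assumptions, and the choice of standard error alone moves the prognostic result with 25 predictors from 51.0% to 87.5%. The trial-level rate also mixes selection bias with the multiplicity that 7.5 accepts, so the per-term rate is the cleaner measure. A fall in the error rate under a patient split cannot be credited wholly to held-out testing, because the split also leaves less data for selection.

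A reader might infer that most null trials would report a false strong result. The documents do not support that. For one outcome it fails when no predictor affects the outcome (24% to 36%). It holds in nearly every version where predictors are prognostic but do not modify treatment. That is the more plausible null for symptom scores, but it is still an assumption.

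**Conclusion.** The concern holds as a fault of inference and labelling in an exploratory objective. The Objective 2 test does not hold a nominal 5% level, and its result should not be called strong evidence. The size is the range in the table, conditional on 10 to 25 candidates, no true interaction and the stated correlations. The per-term range of 34% to 65% applies to sandwich or refit errors only.

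Two further readings go too far. The test does not miss a level stated for it, because 9.2 states none; 5% is borrowed from 9.1.1. Nor does the fault reach the primary analysis in 9.1.1, whose eight interactions are named in advance.

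**What to change.** Keep all data for selection. Report the selected interactions as hypothesis-generating, without Wald tests, and delete the strong-evidence grade from 9.2. This is a change of wording and loses nothing that the present tests validly provide.

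If a strong-evidence grade is wanted, base it only on patients not used for selection. Split or cross-fit by patient, so that a patient's T3 and T4 rows stay together, use patient-clustered standard errors, and correct over the selected terms. The cost is some programming and lower power. The correction is needed, because splitting alone leaves the 8.5% to 25.5% shown above.

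Under either option, list the candidate predictors in advance. If tests are kept, also state the standard error formula and the significance level.

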8.1 Criteria for randomization

Randomization will occur at T2 and T3 study visits. Participants with minimal or modest improvement in pain after the PainGuide run-in (PGIC \geq 2) will be randomized. Participants who have a robust improvement in their pain (PGIC<2) will not be randomized to treatment. These non-randomized participants will still complete the remaining study visits and mini-assessments. In order to assign equal numbers of participants to each of the 4 study interventions, randomization probabilities will account for the fact that certain participants, e.g. because of a contraindication, may be eligible for only 3 of the 4 treatments.

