#### **5.4.2 Inclusion Criteria for Light Phenotyping**

- We will use the definition of chronic low back pain (cLBP) described in the NIH Task Force Report on Research Standards for Chronic Low Back Pain, i.e. low back pain present at least six months, and present more than half of those days.
- Individuals must have a pain interference score of  $\geq 60$  on PROMIS Pain Interference at T1 for inclusion. The normal population mean and standard deviation for the PROMIS Pain Interference measures are 50 and 10 points, respectively. Therefore, participants must be 1 SD above the population mean ( $>=60$ ) for inclusion.
- Individuals must be willing and eligible to be randomized to receive at least three of the four proposed treatments.

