#### **5.4.4 Contraindication to study interventions**

##### **5.4.4.1 Duloxetine**

- Contraindications to receiving duloxetine:
  - Medications such as:
    - Lithium
    - Tramadol (Ultram, Ultracet)
    - St. John's Wort
    - Prochlorperazine (Compazine)
    - Thioridizine (a psychiatric medication)
    - Propafenone or Flecainide (for heart rhythm problems)
    - Ciprofloxacin (Cipro, an antibiotic)
    - Linezolid (Zyvox, an antibiotic)
    - Methylene Blue
    - Cimetidine (Tagamet, for heartburn)
    - Clomipramine (Anafranil)
    - Vortioxetine (Trintellix)
    - SSRIs:
      - sertraline
      - paroxetine
      - fluoxetine
      - escitalopram
      - citalopram
      - fluvoxamine
    - SNRIs:
      - Venlaxaxine
      - Milnacipran
      - Duloxetine
      - Sibutramine
      - Atomoxetine
      - Desvenlafaxine
      - Levomilnacipran
  - Renal dysfunction: Creatinine Clearance <30mL/min or End-Stage Renal Failure
  - Hepatic dysfunction: Liver function tests (LFTs) elevated times 1.5
  - History of allergy to duloxetine
  - History of bipolar disorder

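### Objective 2 ranks all four treatments for every participant, so any optimal-treatment subgroup can include people who were not eligible for, or not willing to take, that treatment at T2

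*SAP*

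**What the plan says.** SAP 9.2 fits a penalized regression to the T3 and T4 outcomes. It then states that "we will also obtain predicted outcomes under each of the four treatment options for all individuals", followed by "We will identify the treatment option which maximizes the predicted outcome for each individual", and that the team will "form up to four subgroups of patients with the same optimal treatment". The use made of the groups is descriptive: "We will conduct descriptive analyses to compare the characteristics of these subgroups and generate hypotheses for future research". SAP 4.2 describes the same objective as finding the best initial treatment for a patient with a given phenotype.

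The adjustment covariates in the 9.2 model are sex, age, BMI, race, education and the baseline outcome. The penalized terms are further clinical or patient-reported predictors and their treatment interactions. No indicator of arm eligibility is named.

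On eligibility, SAP 5.4.2 says: "Individuals must be willing and eligible to be randomized to receive at least three of the four proposed treatments". Protocol 4.1 has the same criterion. Protocol 8.1 expects that certain participants "may be eligible for only 3 of the 4 treatments" and says the randomization probabilities will allow for this. The arm-specific bars are listed separately from the study exclusions, in SAP 5.4.4 and Protocol 4.3, so they close an arm and not the study. The list headed "Contraindications to receiving duloxetine" covers many medications (the named SSRIs and SNRIs among them), renal and hepatic dysfunction, allergy and bipolar history. Acupressure, MBSR and PT/exercise each have a shorter list, mostly about current treatment of the same kind. SAP 5.5 does not mention participants with only three open arms, and SAP 9.2 does not carry them into the analysis.

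**The concern.** The plan recognises, when it randomizes, that some participants have only three arms open to them. It then ranks four arms for those same participants when it looks for the best treatment. Someone barred from an arm, or unwilling to take it, can be labelled as a person for whom that arm is optimal.

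Two things are at stake. First, the prediction behind such a label has no direct support: at the stage where the arm is closed, nobody with that closure was assigned to it. An eligibility term would not repair this, because the combination of ineligible participant and closed arm is empty by design and its interaction cannot be estimated. Second, the subgroup profiles are the part of 9.2 that speaks to the aim set in SAP 4.2. Participants taking a listed antidepressant, for example, could help to shape the profile of patients said to do best on duloxetine, although the plan keeps them out of that arm.

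**Working it through.** The documents give no figure for this step, so there is none to reproduce. The check has two parts.

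**1. The rules side by side**

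- Options ranked: four, for all individuals (SAP 9.2).
- Options a participant must be able and willing to take: at least three (SAP 5.4.2, Protocol 4.1).
- Participants with exactly three: expected (Protocol 8.1).
- Restriction of the ranking to open arms: none found.
- Eligibility term in the model: none named.

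Followed as written, the rule can select a closed arm. I read the selection as the best predicted outcome. The SAP says it is maximized, and a higher PROMIS pain interference score is worse, so that wording needs its own correction. Nothing below depends on it.

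**2. How many participants could be affected, taking duloxetine as the example**

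Inputs:

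- N = 408 randomized participants (SAP 5.4.1).
- q = share ineligible for duloxetine. Not in the documents; assumed.
- s = share of those for whom the model selects duloxetine. Not in the documents; assumed.

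Headline range, with s = 0.25 (one quarter) and q = 0.10 to 0.30:

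- Share of all participants = q × s: 0.10 × 0.25 = 2.5%; 0.30 × 0.25 = 7.5%.
- Count = 408 × 0.025 = 10.2; 408 × 0.075 = 30.6. That is about 10 to 31 people.
- If eligibility is unrelated to predicted benefit, the ineligible share of the duloxetine subgroup is q itself, 10-30%.

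Wider grid, with m = 408 × q rounded to whole participants. The expected number mislabelled is m × s. The probability of at least one is 1 − (1 − s)^m, treating participants as independent.

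| q | m | s = 5% | s = 10% | s = 25% |
|---|---|---|---|---|
| 5% | 20 | 1.0 (0.64) | 2.0 (0.88) | 5.0 (0.997) |
| 10% | 41 | 2.1 (0.88) | 4.1 (0.987) | 10.2 (>0.999) |
| 20% | 82 | 4.1 (0.985) | 8.2 (>0.999) | 20.5 (>0.999) |
| 30% | 122 | 6.1 (0.998) | 12.2 (>0.999) | 30.5 (>0.999) |

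Each cell gives the expected number, with the probability of at least one in brackets. If s = 0 the count is zero for every q. Some mislabelling is therefore likely over most of this grid, but not certain.

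Under a choice restricted to open arms, the count is zero by construction. No sample size, power or alpha figure changes.

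**The case against.** The strongest reply is that this is an exploratory step. Nobody is treated on the labels, and the subgroups serve only description and hypothesis generation. One may fairly ask which phenotype favours which treatment and apply contraindications afterwards. On that reading, a prediction for an ineligible participant means the expected outcome for that phenotype, informed by eligible people with similar predictor values. This stands in part. It limits the weight of the point, and it means the predictions are not wholly without basis. But they do assume that effects carry over to ineligible people with the same measured phenotype, and the trial has no data to test that.

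A second reply is that restricting the choice moves an ineligible participant into the subgroup of their second-best arm, so contraindications would shape the other profiles instead. This is correct, and the fix has to deal with it.

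A third is that the 2.5-7.5% counts labels and does not measure how far any profile is distorted. That also stands: the documents give no basis for sizing the distortion.

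A reader might also infer that the duloxetine subgroup is bound to contain patients who could never receive the drug. The documents do not support this. The number depends on an unstated ineligible share and on the fitted model, and SAP 9.2 allows for fewer than four subgroups, so the duloxetine one may be empty. Some bars are lasting, such as allergy or bipolar history. Others are current medications, including antibiotics, or current courses of therapy that can end, and a participant may have a closed arm through unwillingness alone. Nor is the gap confined to duloxetine.

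**Conclusion.** The point holds. As written, SAP 9.2 can name as optimal an arm that was closed to the participant at T2, in any of the four subgroups, and neither document corrects this. It is a stated rule that conflicts with the eligibility design, and not merely a missing detail.

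The size is uncertain. The figure of about 10-31 of 408 participants rests on the assumed 10-30% ineligible for duloxetine and the assumed one-quarter placement; both would be replaced by the trial's own counts. The consequence is confined to an exploratory, descriptive output. It would be wrong to read it as a threat to the primary Objective 1 analysis or to the correlation-based power statement in SAP 6.1, neither of which uses these subgroups. It still deserves correction before the analysis, because the output is meant to suggest whom to start on which treatment and the correction is cheap.

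**What to change.** Amend SAP 9.2 as follows:

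- Choose each participant's best predicted treatment only among the arms they were eligible for and willing to take at T2.
- Report how many participants had a closed arm, by arm.
- Show the subgroup profiles by eligibility set, including among participants eligible for all four arms, so that those moved to a second-best arm do not distort the other profiles unseen.

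Arm eligibility must already be known at T2 to set the randomization probabilities in Protocol 8.1, so no new assessment should be needed. The cost is a short change of SAP wording, a small change of code and one extra descriptive table. The downside is somewhat smaller subgroups, most of all for the arm that is most often closed, and thinner cells once profiles are split by eligibility set.

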Group Level Analysis. Seed and network-to-whole-brain connectivity maps will be entered into a multiple regression model in SPM with change in pain interference (post minus pre-treatment) as a covariate of interest. Age and sex will be entered as covariates of no interest. Although not the primary objective of Aim 3, we will also conduct exploratory analyses to examine the mechanism of action of specific treatments. Changes in connectivity patterns following each of the phase 1 treatments will be performed using paired sample t-tests in SPM12. Resulting maps are thresholded at $p < .001$ uncorrected voxel threshold with $p \leq .05$ FDR significance corrected for multiple comparisons.

Graph Theory Analyses. Using Graph Theory Analyses the brain is defined as a network of 264 non-overlapping nodes (10 mm spheres) connected by edges or links.^{161,162} These nodes and the preprocessed fMRI data are entered into the Conn functional connectivity toolbox to create Fisher z-transformed bivariate correlation (Pearson's r) matrices (264 x 264) for each participant. To exclude weak or spurious connections, matrices are thresholded beginning with the strongest 5% connections and proceeding in steps of 5% up to 40% density, resulting in binary undirected graphs containing the most significant edges. Using the Brain Connectivity Toolbox,¹⁶³ we will calculate the following graph theoretical measures to assess global (efficiency, modularity, rich-club) and nodal (hub status) network properties, as previously published.¹⁶⁴ To assess hub status, we will calculate eigenvector centrality which takes into account the connectedness of a node, in addition to the connectedness of that node's neighbors. Hub status will be assigned to a node if the eigenvector centrality is greater than one standard deviation above the group mean.^{165,166}

Group Level Analysis. We will determine if hub status and rich club organization predicts treatment response. Individual hub measures will be entered into regression analyses to predict ($p < .05$) association with change in pain interference pre- versus post-treatment.

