### 6.1 Power for explaining treatment effects

Consider a regression model for correlating within-patient improvement (primary: change in PROMIS Pain Interference; secondary: change in PEG, PGIC; many others as exploratory, see below for details) due to one of the 4 main treatments with a phenotypic variable. Using a two-sided test for correlation at 5% significance level we conclude that we will have the power of at least 80% to detect correlations of 0.28 or higher, conservatively assuming the model is applied to one randomized treatment segment with 102 patients. This corresponds to first phase or second phase treatment in one of the 4 treatment groups, and a model based on the light phenotyping target patient group of 408 total. Similar analysis for the smaller subgroup based on 40 patients with available deep phenotyping for a specific treatment and segment shows that correlation of 0.42 or higher will be detectable with 80% power. This is well within reach as evidenced by available literature on the association between treatment effects and phenotype variables. For example, mindfulness and pain responses showed correlations of 0.43-0.51 in prior reported studies. Our previous studies of the association between pain centralization and analgesic responses in knee osteoarthritis showed similar or higher correlations.

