## **8.2 Derived variables**

The study's primary and secondary endpoints are each scored as recommended by instrument authors. The PROMIS-based measures will be derived in Qualtrics using a tool released by HealthMeasures.net. The PROMIS composite scores have a population mean and standard deviation equal to 50 and 10 points, respectively. The Oswestry Disability Index is calculated by summing the individual item scores (values ranging from 0 – 5) and multiplying by 2. Its range runs from 0 to 100.

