### 9.3 Objective 3 Analysis Plan

**Objective 3:** Identify the mechanisms that explain the causal treatment effects.

The primary analysis for the exploratory objective 3 (specific aim 2) will involve a series of mediation analyses in order to identify the mechanisms that underlie the differential treatment responses. This analysis will use light phenotyping data from T2 and the interim assessment conducted at the midpoint of the first-stage treatment period. Second-treatment stage data will not be used for this analysis. Investigators did not propose a light phenotyping-based mediator for the Duloxetine treatment. Thus, a mediation analysis based on light-phenotyping data will not be carried out for this study arm.

The study does not include a control group since each of the four therapies have been previously shown to be effective for treating cLBP. As a result, the mediation analyses will be conducted by treatment group. Within each treatment group, the proposed treatment modifier will play the role of the exposure in the mediation analysis. Hypothesized mediators were determined by the study investigators and are listed in Table 6 by treatment arm.

For example, consider the PT/Exercise treatment group. Investigators expect that individuals who both receive the PT/Exercise treatment and have lower self-perception of their own efficacy will respond better to the PT/Exercise intervention and have lower PROMIS Pain Interference scores at follow up. They believe that this effect is attributable in part to changes in the patients fear avoidance beliefs and avoidance behaviors. The mediation analysis will assess whether greater pain catastrophizing is associated with a greater reduction in fear avoidance beliefs, which leads to greater improvement in pain interference scores.

The outcome measure for each mediation analysis will be the PROMIS Pain Interference score measured at T3. The exposures and mediators will be measured at T2 and the first treatment-stage midpoint, respectively.

*Table 6 Hypothesized Mediation Analyses by Treatment.*

Treatment	Mediation Analysis Exposure (X)	Expected treatment mediator (M)
MBSR	PROMIS Pain Catastrophizing	Experiences Questionnaire Score
PT/Exercise	Pain Self-Efficacy Score	Fear Avoidance Beliefs Questionnaire
Acupressure	Fibromyalgia Screening Score	GSS-8

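### Exploratory Objective 2 labels as optimal the treatment with the highest predicted pain interference, although a lower score is better (probably a wording slip)

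*SAP*

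**What the plan says.** SAP section 9.2 sets out an exploratory analysis in which "we will fit regularized regression models for the primary pain outcome (PROMIS pain interference score) using observations from time points T3 and T4". The modelled quantity is the score itself at T3 or T4, with the T2 value among the baseline covariates. The analysis is repeated for PEG and PGIC.

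After fitting, the SAP obtains each patient's predicted outcome under all four treatments and continues: "We will identify the treatment option which maximizes the predicted outcome for each individual". Patients who share a selected arm form one of up to four optimal-treatment subgroups. These are compared descriptively to find "baseline patient phenotypes which may be useful for determining optimal initial treatment".

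On scoring, SAP section 8.2 says only that the "primary and secondary endpoints are each scored as recommended by instrument authors".

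**The concern.** A high pain interference score means more interference. Selecting the arm with the highest predicted score therefore selects the arm from which the model expects the poorest result, and the SAP then calls that arm optimal.

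SAP section 4.2 words Objective 2 as finding the best initial treatment for a given phenotype, and this is the only step in section 9.2 that names a best treatment for each patient. An analyst who codes the sentence as printed would produce plausible-looking subgroups that point the wrong way. Section 9.2 contains no check that would expose the reversal.

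**Working it through.** The plan gives no figure to reproduce here. The check compares the direction of the outcome with the direction of the rule.

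**1. What is predicted.** The section 9.2 model is for the expected score at time t. It is not a model for change or for improvement.

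**2. Which direction is good.**
- SAP section 5.4.2: entry needs a score of at least 60, since "participants must be 1 SD above the population mean". High scores mark the patients who need treatment.
- SAP section 9.3: patients expected to do well on physical therapy are those who "respond better to the PT/Exercise intervention and have lower PROMIS Pain Interference scores at follow up".
- PGIC: SAP section 6 treats a rating of 1 as the greatest improvement, and Protocol section 8.1 treats a rating below 2 as a robust improvement. Lower is better.
- PEG: neither document states a direction. Lower-is-better is inferred from its description as pain intensity.

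**3. Does any passage reverse the sign?** Three places might.
- Section 8.2 follows the instrument authors and mentions no reversal.
- SAP section 6.1 speaks of "within-patient improvement (primary: change in PROMIS Pain Interference", but this belongs to the power calculation and fixes no sign.
- Protocol section 10.2.1 gives a sign for change in its imaging models, "with change in pain interference (post minus pre-treatment) as a covariate of interest". On that scale, too, lower is better.

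**4. Would modelling change help?** For patient i and treatment a, write P(a) for the predicted score and B for that patient's T2 score.
- Post minus pre: P(a) − B. B is the same for all four treatments, so the arm with the largest value is still the arm with the largest P(a).
- Pre minus post: B − P(a). The arm with the largest value is the arm with the smallest P(a).

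Simulated data for 200,000 patients gave the same arms in 100% of cases on both counts. Only pre minus post would make the printed rule correct, and section 9.2 does not define that outcome.

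**5. Consequence without further assumptions.** If the four predictions are not all equal, the largest and smallest belong to different arms, so the printed rule never selects the arm with the lowest predicted score. If no interaction enters the model, the predictions differ only through the treatment main effects. All patients then fall into one subgroup, labelled with the arm that has the highest adjusted mean pain interference.

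**6. Illustration under assumed inputs.** The documents give neither the spread of individual treatment effects nor the accuracy of prediction. Assume that each patient's true deviations under the four treatments are independent and normal with SD s, and that predictions correlate r with them. Selecting at random would find the best arm for 25% of patients. With 2,000,000 simulated patients per value of r:

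| r | Max rule names truly best arm | Max rule names truly worst arm | Min rule names truly best arm |
|---|---|---|---|
| 0.3 | 15.3% | 36.6% | 36.6% |
| 0.5 | 9.6% | 46.0% | 46.0% |
| 0.8 | 2.7% | 65.1% | 65.1% |

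The Monte Carlo standard error is at most 0.04 percentage points.

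The mean true difference between the arms named by the two rules is 2 × E[max of 4 standard normals] × r × s = 2 × 1.0294 × r × s:
- r = 0.3, s = 1 point: 2 × 1.0294 × 0.3 × 1 = 0.62 points.
- r = 0.8, s = 3 points: 2 × 1.0294 × 0.8 × 3 = 4.94 points.

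The simulated differences per unit SD (0.616, 1.030, 1.646) agree with the formula (0.618, 1.029, 1.647).

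**The case against.** The strongest reply is that the passage corrects itself. It calls the selected arm optimal, and the next section uses the right direction for the same score. On this reading, to maximize the outcome means to obtain the best outcome, and harm arises only if someone codes the verb against its own label. That is very likely the intent. It does not settle the matter, because the sentence follows an explicit definition of the outcome as the raw score, and an analysis plan should be codable as it stands.

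A second reply is that little depends on this step. Section 9.2 opens by restating Objective 2 as finding additional predictors of differential response. Variable selection and Wald tests meet that aim, and neither depends on direction. SAP section 11 also plans separate exploratory tailoring of the treatment regimens. This stands, and it limits the weight of the point. The subgroup step remains the only part of section 9.2 that names a best arm for each patient.

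Two narrower replies also stand in part. The Protocol's sign for change comes from imaging models, and elsewhere the Protocol codes response as percentage improvement or reduction, so the sign convention is not uniform. That favours stating the sign in section 9.2. The percentages in the illustration follow from assumed inputs and say nothing specific about this trial; the reversal itself needs none of them.

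**Conclusion.** The point holds. As written, the rule gives each patient the arm with the worst predicted pain interference and calls it optimal. The reversal is complete relative to the model's own predictions whenever those differ, and this rests only on the direction of the scale, which the documents fix for PROMIS pain interference and PGIC. For PEG it rests on an inferred direction. The illustrative range of 0.62 to 4.94 points depends on the assumed SDs and correlations.

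The practical reach is modest. The step is exploratory and descriptive. The primary analysis in section 9.1, the interaction tests in section 9.2, the sample size and participants' treatment are unaffected, and the labels can be recomputed. It should still be corrected, because it is an operative rule that, if followed, would give an inverted answer to a stated objective.

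**What to change.** In SAP section 9.2, replace maximizes with minimizes in the selection rule, and state that lower is better for PROMIS pain interference and PGIC. State the scoring direction of PEG as well, since neither document gives it, and apply the rule accordingly.

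Alternatively, for the score outcomes, define the predicted quantity as improvement, T2 minus follow-up, with the sign written out, and keep maximizes.

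The cost is one word or one sentence. No new data, model or analysis is needed. The analysis code should be checked against the corrected sentence.
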